## 1. BACKGROUND

### 1.1 Study Disease

Radical prostatectomy for localized prostate cancer provides excellent cancer control, but comes at a significant detriment to health related quality of life, primarily in the domains of sexual and urinary quality of life. A recent population based study reported that 76% and 87% of men could not attain erections sufficient for intercourse at 5 and 15 years after surgery, respectively. The greatest decline in erectile function occurs immediately after surgery, with some recovery in the next 1-2 years. However, potency never returns to baseline and there will always be some degree of permanent loss in erectile function. Even with the influx of minimally invasive surgery, we continue to see a significant proportion of men with post-surgical impotence.

Urinary incontinence following surgery have been as high as 50%. This undesirable side effect of treatment can significantly interfere with quality of life. Although most men improve with time, up to 10% can have persistent leakage and may seek further surgery for moderate to severe urinary incontinence. Even men with mild incontinence may still be bothered by having to wear even a pad, which may interfere with their quality of life and result in less satisfaction with treatment outcomes. Men undergoing minimally invasive surgery have similar levels of bother related to incontinence post prostatectomy, suggesting that the minimally invasive nature of the procedure does not preclude them from the side effects of urinary incontinence.

These issues pose a significant burden to health related quality of life for men undergoing surgery for prostate cancer. Given the prevalence of prostate cancer, they also have a significant public health impact. Any treatments or techniques that can reduce the magnitude or improve the recovery of these functional outcomes would be a welcome addition.

## 1.2 Study Interventions

Placement of amnionic membranes over the neurovascular bundle after bilateral nerve sparing robotic radical prostatectomy

## 1.3 Rationale

A recent study reported that the use of dehydrated human amnionic membrane allograft placed over the neurovascular bundle during robotic assisted radical prostatectomy accelerated an early return to potency. These findings have resulted in a wide adoption of this technique by many surgeons and patients. However, these findings are observational and have never been validated in a randomized trial.

## 1.4 Preliminary Studies

Patel et al conducted an interventional trial wherein men with prostate cancer undergoing Robot Assisted Radical Prostatectomy (RARP) were implanted with a dehydrated human amnion chorion allograft (dHACM) around the neuro-vascular bundle. The subjects were previously continent (American Urological Association Symptom Score <10) as well as potent (Sexual History Inventory for Men Score >19).

This study showed that dHACM placement significantly facilitated early return to potency and continence. Continence at 8 week returned in 81.0% of the dHACM group and 74.1% of the no-dHACM group ( $p = 0.373$ ). Mean time to continence was enhanced in dHACM patients (1.21 months) versus no-dHACM patients (1.83 months;  $p = 0.033$ ). Potency at 8 weeks returned in 65.5% of the dHACM patients and 51.7% of the no-dHACM group ( $p = 0.132$ ). Mean time to potency was enhanced in dHACM group, (1.34 months), compared to no-dHACM (3.39 months;  $p = 0.007$ ). Graft placement enhanced mean time to continence and potency

As a result of this study many centers have begun using amnionic membranes with the hope that they will induce an earlier recovery of potency and urinary control. Furthermore, many patients have been requesting to have amniotic membranes placed at the time of surgery for similar beliefs regarding it's potential utility for functional recovery. However, a major limitation of this study is that it was conducted as an observational study with a computer matched cohort rather than a randomized trial, leaving a significant potential for bias. As a result, the findings should be considered hypothesis generating at best and further validation should be required in randomized studies before this technique can be considered in contemporary clinical practice.

## 2. HYPOTHESIS

The use of dehydrated human amniotic membrane allograft will reduce the decline in erectile function (as measured by SHIM score) at 12 months after robotic assisted radical prostatectomy (RARP).

## 3. OBJECTIVES

### 3.1 Primary Objective

To see if the use of dehydrated human amniotic membrane allograft improves erectile function recovery (as measured by SHIM score) at 12 months after robotic assisted radical prostatectomy (RARP) compared to a control group with no allograft.

### 3.2 Secondary Objectives

- Among men with a SHIM greater than or equal to 17 at baseline, to compare the proportion of men in each group with mild ED or better, defined by a SHIM greater than or equal to 17, at 3, 6, 9 and 12 months post RARP
- Among men with a SHIM greater than or equal to 17 at baseline, to compare the proportion of men in each group who are able to achieve an erection sufficient for intercourse more than 50% of the time at 3, 6, 9 and 12 months post RARP.
- Among men with a SHIM greater than or equal to 17 at baseline, to evaluate the proportion of men in each group who require the use of more invasive erectile aids (intra-cavernosal injection, vacuum pump, or penile prosthesis) at 3, 6, 9, and 12 months post RARP
- Rates of urinary control as measured by no pads per day at 3, 6, 9, and 12 months
- To compare 5 year rates of prostate cancer recurrence between the two groups

## 4. STUDY DESIGN

This is a phase 2 prospective randomized trial investigating the impact of amniotic membrane placement over the neurovascular bundles after bilateral nerve sparing robot assisted radical prostatectomy on potency. The study will have a control arm that will follow standard of care surgery, without placement of any membranes.

#### **4.1 Accrual goal**

70 men will be allocated to each arm. The rationale for this number is provided in the sample size section of the statistical analysis (Section 10.5)

#### **4.2 Duration of Study Participation**

The research study will involve follow up every 3 months for the first 12 months. After this we will follow patients annually with PSA measurements and an assessment of any secondary therapies for 5 years post surgery.

#### **4.3 Study Randomization**

Randomization of study patients will be done in equal proportion to Arm I (membrane placement) and Arm II (no membrane placement, standard of care surgery) using a permuted block design stratified by baseline SHIM score (<17 vs.  $\geq 17$ ), and use of **ANY** erectile aids (Yes vs. No) in the last 3 months.

Randomization lists for each stratum will be prepared by SCCC Biostatistics prior to the first patient enrollment and provided to the SCCC CRS-Informatics office where they will be programmed and customized as per randomization requirement using the CIERRA system. Members of the study team, including those responsible for patient enrollment, will not have access to the randomization lists.

After each patient's study eligibility is confirmed and the informed consent is signed, CRS coordinators will enter the required patient information into the CIERRA system in order to register the patient. The CRS coordinators will receive the designated patient ID, study arm, randomization number, and randomization date. CRS coordinators will print the randomization confirmation form from the CIERRA system and place it in the patient's research chart and then notify the requesting member of the study team of the treatment assignment for the new randomized patient.

#### **4.4 Follow Up and Analyses**

Patients will be followed up every three months ( $\pm$  1 month) for a total of one year. This follow up schedule meets the current standard of care after radical prostatectomy. At each follow up a serum PSA will be assessed for recurrence on prostate cancer. To investigate primary and secondary endpoints a self-reported validated questionnaire will be provided assessing measures of potency. Finally, the use of pads for urinary leakage will be

assessed at each time point. After the first year, there will be annual follow up with PSA measurements and an assessment of any secondary therapies for 5 years. Further details regarding the primary and secondary endpoints can be found in Section 3. The analyses will be performed as an intention to treat analysis. More details regarding the analyses of primary and secondary endpoints can be found in Section 10.

## 5. STUDY ENTRY AND ENROLLMENT AND WITHDRAWAL

### 5.1 Nerve sparing robotic assisted radical prostatectomy

In the USA, enthusiasm for the robotic- assisted technique currently overshadows conventional laparoscopic radical prostatectomy. Two series in the US have demonstrated the successful transfer from the open to laparoscopic technique by aid of the robotic device. Similar functional and oncological outcome have been noted between open and robotic prostatectomy,. However, the robotic approach has the advantage of faster recovery and less blood loss. As a result the majority of the University of Miami cases are done robotically.

The operative procedure for nerve sparing RARP has the following steps:

- Incision is done on the peritoneum overlying the vas deferens and seminal vesicle.
- Seminal vesicle and the vas deferens are dissected out bilaterally.
- The plane below the prostate and above the rectum is developed towards the apex of the prostate.
- Anterior dissection (dropping) of the bladder is performed and the endo-pelvic fascia is opened bilaterally.
- Junction of the prostate and bladder is identified.
- Incision is taken at the bladder neck both anteriorly and posteriorly.
- The neuro-vascular bundle is identified and dissected from the prostatic pedicle.
- Prostatic pedicle will be ligated and cut with the use of hemo clips.
- Then the apical dissection will be conducted by dividing the dorsal venous complex and urethra
- A *vesico-urethral anastomosis* will be conducted and will be checked for no leakage.
- If indicated a bilateral pelvic lymph node dissection may be performed.

## **5.2 Use of membranes during the procedure**

The placement of amniotic membranes to enhance the recovery of potency and urinary control is available at many centers, despite the lack of proper validation of this technique. The procedure has been performed at UM, as well as other community based and academic practices around the nation. Amniotic membranes will be placed over the neurovascular bundle after extirpative RARP, and before the urethrovesical anastomosis. The membrane will cut into two longitudinal pieces and it will be placed over each neurovascular bundle separately. The membrane will be accessed from the Um tissue bank who will provide it to the OR (Operatory room) to ensure availability during cases. The membrane will be identified by a stock number on the packaging but not in the membrane itself.

## **5.3 Follow up**

Measurement of PSA is a cornerstone in follow-up after treatment. Patients will be followed-up as per the usual standard of care with a PSA every 3 months. PSA measurement and history and physical are recommended at 3, 6, 9 and 12 months ( $\pm$  1 month) postoperatively, and as per the clinician's discretion afterwards. During each follow up functional assessment for urinary and sexual quality of life will be performed as per the study calendar. After the first year, follow up will occur annually with a PSA measurement and an assessment of any secondary therapies for 5 years post surgery. If a patient is unable to continue a minimum annual follow after the first year post surgery at UM, then a call to inquire about the receipts of any salvage therapies and measurement of serum PSA will suffice.

## **5.4 Erectile rehabilitation**

Many men undergo a procedure called penile rehabilitation, where they will use oral phosphodiesterase inhibitors (PDE5i) after surgery to help improve the recovery of potency. In some cases, oral medications will not be enough and further intervention is required in the way of vacuum pumps, intracorporeal injections, or even penile prosthesis. These medications may impact the association between membrane use and potency and therefore every consideration should be made to balance the use of these medications between the trial arms. To ask men to abstain from these medications would be unethical. However, to attempt to standardize the use of these medications between the arms may be difficult due to the cost of these medications and the variable coverage that different insurance companies provide for their usage, notwithstanding the variable views men may have towards using these medications.

We will offer men a standard of care penile rehabilitation program post RARP using oral PDE5i therapy, with the option of advancing to other

interventions (such as intracorporal injections, vacuum pumps, or penile prosthesis) after 3-6 months post RARP if the oral medications are not sufficient. We will stratify the randomization of men based on their current usage of oral PDE5i medications between the arms. We will also ascertain each man's ability to use these medications post-surgery (based on willingness to use and ability to cover the cost of the medication) to further balance the usage of these medications as best possible between the arms. Finally, we will ascertain the frequency and quantity of use of these meds by each man at all follow up intervals so we can control for their use during the analysis.

### **5.5 Study Entry**

Study entry, as used in this protocol, will be defined as a subject signing informed consent. Study enrollment, as used in this protocol, will be defined as the investigator's confirmation of the subject's eligibility by signing an eligibility checklist. As per University of Miami policy, each study participant who signs an informed consent form should be entered into the Velos system within 48 hours of consent being obtained

### **5.6 Enrollment Procedure**

As per UM/SCCC Clinical Research Services policy, a CRS director or designee must also review eligibility. The investigator or study coordinator will provide the following to a CRS representative

- Completed and signed protocol-specific eligibility checklist;
- All pages of the original signed informed consent forms (ICFs), including HIPAA Form B;
- Relevant source documents such as: subject medical history and physical exam, admission or discharge notes, diagnostic reports, pathologic confirmation of diagnosis, and relevant subject-specific written communication.

### **5.7 Cancellation Guidelines**

The following are reasons for withdrawal of subjects from the study:

- A subject does not meet the eligibility criteria, (the subject will be considered a screen failure).
- A subject withdraws consent,
- A subject dies during protocol participation or
- A study investigator decides the subject should be withdrawn from the study (e.g. subject non-compliance)

Regardless of reason for withdrawal, once a patient has been randomized to an arm, an intention to treat analysis will be performed.

## **6. PATIENT SELECTION/ELIGIBILITY CRITERIA**

### **6.1 Inclusion (Eligibility) Criteria**

- Men age 40-80 with localized prostate cancer who are undergoing bilateral nerve sparing RARP at the University of Miami

### **6.2 Exclusion (Eligibility) Criteria**

- Men with poor urinary control at baseline requiring the use of pads for leakage
- Previous treatment for prostate cancer
- Previous history of pelvic radiation
- Men who are using non-oral erectile aids such as vacuum pump, intra-cavernous injections, MUSE, penile prosthesis.

### **6.3 Gender and Ethnicity**

Prostate cancer is a disease of adult men, with exceptionally few diagnosed at 35 years of age. Therefore, women and children are not candidates for this protocol. Based on standard NIH definitions, we estimate that approximately 40% of patients will be White, 24% African American, 35% Hispanic and 1% other at the University of Miami.

## **7. CLINICAL, RADIOLOGICAL, LABORATORY AND SURGICAL EVALUATIONS**

### **7.1 Screening Evaluations**

- History and physical exam within 3 months prior to protocol enrollment.
- Baseline SHIM and EPIC 26 Scores within 3 months of RARP

### **7.2 Evaluations During Intervention**

- SHIM and EPIC 26 Scores at 0, 3, 6, 12 months ( $\pm$  1 month).
- Urinary incontinence measured by the number of pads used per day at 3, 6, 9 and 12 months ( $\pm$  1 month).
- Serum PSA every three months ( $\pm$  1 month) for first year post surgery, and then annually for 5 years.

### **7.3 Early discontinuation of study participation**

Subjects that discontinue participation in part of or all the interventions in this study due to progression or other (patient or physician decision) reasons will be followed for clinical data and analyzed by intention to treat. Those who experience a biochemical or clinical recurrence and undergo radiation will be analyzed by intention to treat and their analysis adjusted for the receipt of secondary treatments. There will be no stopping rules for safety, as previous observational studies have suggested no increased risk of any adverse events with placement of membranes during the surgery. All adverse events will still be reported, as discussed in Section 8.

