## 10. STATISTICAL CONSIDERATIONS

This is a blinded two-arm randomized phase 2 trial. Patients will be randomized in a ratio 1:1 to study arms, the experimental Arm I (membrane placement) and control Arm II (no membrane placement, standard of care surgery), using a permuted block design stratified by baseline SHIM score (<17 vs. >=17), and use of ANY erectile aids (Yes vs. No) in the last 3 months.

All analyses will be performed as an intention to treat and as per Protocol. Although there is no data to suggest an increased risk of any potential adverse effects with placement of a sling, we will monitor adverse events as per section 10.7.2. An interim analysis of the primary efficacy endpoint, change in SHIM score, will be performed as part of the analysis plan as described in section 10.7.3..

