### 10.7.2 Safety: Early stopping due to adverse events

The interim monitoring guidelines for stopping due to adverse events appearing in this section will be applied separately to each arm

- If a treatment-related (possible, probable, or definite) death (grade 5 toxicity) occurs, enrollment will be suspended and continuation of the study will be reassessed by the DSMC.
- **Unacceptable adverse event** is defined as any grade 3, 4, or 5 treatment-related possible, probable, or definite) adverse event, excluding grade 3 xxxx revolved or down grade to grade 2 with 14 days.
- Unacceptable adverse event is expected to occur in no more than 10% of patients. If there is evidence that the true rate of unacceptable adverse event exceeds 15%, then accrual to the particular study arm should be suspended. Specifically, we suggest as a guideline for early termination of accrual to a particular arm a posterior probability of 90% or higher that the true rate exceeds 15%. The table below shows specific instances where this guideline is met, suggesting early termination, and due to evidence of excessive unacceptable adverse event.

Number of patients with unacceptable adverse event #	Patients evaluated for adverse event	Observed adverse event rate >=
3	4 to 7	43%
4	8 to 12	33%
5	13 to 17	29%
6	18 to 22	27%
7	23 to 27	26%
8	28 to 32	25%
9	33 to 38	24%
10	39 to 43	23%
11	44 to 48	23%
12	49 to 54	22%
13	55 to 60	22%
14	61 to 65	22%
15	66 to 69	22%

#: treatment-related (possible, probable, or definite) grade 3 or higher adverse event, excluding grade 3 xxxx revolved or down grade to grade 2 with 14 days.

To illustrate the stopping guidelines, suppose that 7 evaluable patients in the have been assessed for adverse event and 3 of them have experienced unacceptable grade 4 treatment-related adverse event. (See row 1 of the above table.) Under this circumstance, the observed rate of unacceptable adverse event is 43%, resulting in a posterior probability of 92.1% (not shown) that the true underlying rate exceeds 15%, thereby suggesting early termination.

Posterior probabilities for the above table are calculated under a weak prior beta distribution with parameters  $\beta_1 = 0.2$  and  $\beta_2 = 1.8$ , which corresponds to an expected rate of 10% based on very limited information, roughly equal to having studied 2 patients. This prior distribution implies also a priori chance of only 21.6% that true rate is 15% or greater

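### Section 7.3 rules out safety stopping rules that Section 10.7.2 sets, and the event counted in 10.7.2 contains an unfilled placeholder

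*Combined protocol and SAP*

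**What the plan says.** Section 7.3, on early discontinuation, says: "There will be no stopping rules for safety, as previous observational studies have suggested no increased risk of any adverse events".

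Section 10.7.2 is headed as early stopping for adverse events and contains two provisions.

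- Death: "If a treatment-related (possible, probable, or definite) death (grade 5 toxicity) occurs, enrollment will be suspended", after which the DSMC reassesses whether the study continues.
- Adverse event rate: the suggested guideline is "early termination of accrual to a particular arm a posterior probability of 90% or higher that the true rate exceeds 15"%. A table of counts follows, from 3 events in 4 to 7 patients up to 15 events in 66 to 69.

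Both work by arm: "The interim monitoring guidelines for stopping due to adverse events appearing in this section will be applied separately to each arm". Section 10 relies on them ("we will monitor adverse events as per section 10.7.2"). Section 10.7.1 refers the DSMC to them as guidelines for its consideration and leaves suspension or termination to the DSMC.

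The counted event is any treatment-related grade 3, 4 or 5 event, "excluding grade 3 xxxx revolved or down grade to grade 2 with 14 days". The table footnote repeats the gap: "treatment-related (possible, probable, or definite) grade 3 or higher adverse event, excluding grade 3 xxxx revolved". The expected level is also given: "Unacceptable adverse event is expected to occur in no more than 10% of patients".

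**The concern.** There are two drafting defects.

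First, someone who reads Section 7.3 learns that no safety stopping rules exist, while someone who reads Section 10.7.2 finds two. An ethics board, a DSMC member or a coordinator could leave with opposite answers.

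Second, the numerator of the posterior guideline is incomplete. The grade (3), the outcome (resolved, or down to grade 2) and the window (14 days) can be read, but the type of event cannot. Two people could classify the same resolved grade 3 infection differently, and infection is the one event that Section 8 anticipates from the membrane. What is at stake is whether the guideline is applied consistently. The primary endpoint and its analysis are not affected.

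**Working it through.** **1. The two sections side by side.** Section 7.3 denies stopping rules on the ground that earlier observational studies showed no added risk. Section 10 starts from the same premise and reaches the opposite result: events will be monitored under 10.7.2. The death provision in 10.7.2 says that enrollment will be suspended, which is a stopping rule in plain terms. Both are current text; neither comes from a summary of changes.

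**2. Reproducing the plan's own figures.** Inputs from 10.7.2: prior Beta(0.2, 1.8), limit 15%, threshold 90%. With x events in n patients the posterior is Beta(0.2 + x, 1.8 + n − x), and the guideline looks at P(rate > 0.15).

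- Prior: P(rate > 0.15) = 0.216 (plan: 21.6%).
- x = 3, n = 7: Beta(3.2, 5.8) gives 0.921 (plan: 92.1%).

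**3. What the placeholder can change.** Take 7 patients in an arm, two with treatment-related grade 4 events and one with a treatment-related grade 3 event that resolved in 10 days (an invented example). If the third event counts, the count is 3 and the first table row is met. If it is excluded, the count is 2 and the row is not met. Persistent grade 3 events and grade 4-5 events are counted either way.

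**4. How often it would matter.** The documents give no rate for transient treatment-related grade 3 events, so the rates here are assumptions. The chance that one arm ever reaches the printed counts was computed by exact recursion, with a look after each patient from n = 4 to 69 and at most one counted event per patient.

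| Rate of other counted events | Transient events excluded | Counted, +1 point | Counted, +2 points | Counted, +5 points |
|---|---|---|---|---|
| 10% (the plan's ceiling) | 6.4% | 9.1% | 12.5% | 27.7% |
| 5% (assumed) | 0.6% | 1.1% | 1.8% | 6.4% |

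At low total rates the chance is about 0.004% (rate 1%), 0.03% (2%) and 0.1% (3%).

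**5. The printed table against the 90% threshold.** At the upper limit of each of the 13 rows, 10 rows reach 0.90 and three fall just short.

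| Events | Printed upper limit | Posterior there | Largest n that reaches 0.90 |
|---|---|---|---|
| 9 | 38 | 0.8953 | 37 |
| 12 | 54 | 0.8998 | 53 |
| 13 | 60 | 0.8950 | 59 |

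With strict limits the crossing chance at a 10% rate is 6.3%, against 6.4% with the printed table.

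**The case against.** The best defence is that 10.7.2 offers only guidelines, that Sections 10 and 10.7.1 both lead the reader there, and that the sentence in 7.3 is an obvious leftover. Much of this stands: which text is meant to operate is not in serious doubt, and the posterior guideline is advisory. It does not rescue 7.3, because the death provision is worded as mandatory and the 7.3 sentence carries no qualification.

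On the placeholder, the defence is that most of the exclusion is legible and the effect is small. That also stands. The larger figures above come from setting other events at the plan's ceiling or adding 5 points, for which the documents give no support. Section 8 suggests that membrane-related events are rare, and at a total rate of 3% or less the placeholder makes almost no difference. Those low rates are themselves an assumption, and they would not apply if surgical complications were attributed to treatment. `xxxx` carries no redaction mark and sits beside other drafting slips, so it reads as an unfilled template field.

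A reader might infer that patients are left without safety oversight. The documents do not support that. Section 9 sends every grade 3-5 event to the DSMC whatever its attribution and requires a report if grade 3 or 4 events become more frequent. Section 10.7.1 gives the DSMC responsibility for suspending or terminating the study.

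**Conclusion.** The point holds as a contradiction plus an incomplete event definition, both in current text. It should be corrected, but its consequence is minor. The contradiction has no numerical effect. The placeholder leaves open only whether a transient treatment-related grade 3 event counts toward an advisory guideline. Under the assumed rates this moves the per-arm chance of meeting the guideline from 6.4% to 9.1% (10% base plus 1 point), and the effect is negligible if events are rare.

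Two further inferences go beyond the documents. One is that the rest of the safety rule is fully defined. The placeholder does not touch grade 4-5 events or the death provision, but both depend on the term treatment-related. The rule applies to each arm, the control arm receives no membrane, and Section 8 says that surgery is not the intervention under assessment. What treatment-related means in the control arm is not explained. The other is that the stopping table is correct as printed: three upper limits fall slightly below the stated 90%, although the practical effect is slight.

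**What to change.** - Section 7.3: replace the sentence on stopping rules with a reference to Section 10.7.2.
- Section 10.7.2, definition and table footnote: either name the grade 3 events that are excluded when they resolve or drop to grade 2 within 14 days, or delete the exclusion so that all treatment-related grade 3-5 events count.

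Deleting the exclusion is the more cautious choice. Its price is that the advisory guideline is met somewhat more often, by the amounts shown above. The choice belongs to the investigators and the DSMC.

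While the section is open, the three upper limits could be set to 37, 53 and 59, with the following rows starting one patient earlier, and a line could say what treatment-related means in the control arm.

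The cost is a few lines of text in one amendment, with no added patients, visits or analyses.
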